## **Appendix B: Prohibited Drugs Affecting the QT interval**

### **Drugs Accepted by the QTDrugs.org Advisory Board of the Arizona CERT to have a Risk of Causing Torsades de Pointes and Prohibited in this Study**

Generic Name	Clinical Use
Amiodarone	Anti-arrhythmic
Arsenic trioxide	Anti-cancer
Astemizole	Anti-histamine
Bepridil	Anti-anginal
Chloroquine	Anti-malarial
Chlorpromazine	Anti-psychotic / Anti-emetic / Schizophrenia
Cisapride	GI stimulant / heartburn
Clarithromycin	Antibiotic
Disopyramide	Anti-arrhythmic
Dofetilide	Anti-arrhythmic
Domperidone	Anti-nausea
Droperidol	Sedative / Anti-nausea
Erythromycin	Antibiotic / GI stimulant
Halofantrine	Anti-malarial
Haloperidol	Anti-psychotic / schizophrenia
Ibutilide	Anti-arrhythmic
Levomethadyl	Opiate agonist / pain control
Mesoridazine	Anti-psychotic
Methadone	Opiate agonist / pain control
Pentamidine	Anti-infective
Pimozide	Anti-psychotic
Probuconol	Anti-lipemic
Procainamide	Anti-arrhythmic
Quinidine	Anti-arrhythmic
Sotalol	Anti-arrhythmic
Sparfloxacin	Antibiotic
Terfenadine	Anti-histamine
Thioridazine	Anti-psychotic

### Appendix C: List of co-medications with known CYP3A4 interaction

The following medications should be used with caution. This is not a comprehensive list of medications. Please contact the medical monitor with any questions.

Drug Name	Class
Afentanil	Analgesic
Alprazolam	Benzodiazepine
Budesonide	Corticosteroid
Buspirone	Anxiolytic
Carbamazepine	Anti-epileptic
Chlorpheniramine	Anti-histamine
Clarithromycin	Antibiotic
Diazepam	Benzodiazepine
Ebastine	Anti-histamine
Efavirenz	Anti-viral
Eletriptan	5-HT agonist
Everolimus	Immune modulator
Felodipine	Calcium channel blocker
Imatinib	Anti-leukemia
Itraconazole	Anti-fungal
Lovastatin	HMG CoA reductase inhibitor
Midazolam	Benzodiazepine
Nisoldipine	Calcium channel blocker
Phenobarbital	Barbiturate
Phenytoin	Anti-epileptic
Rifampin	Antibiotic
Ritonavir	Anti-viral
Sildenafil	PDE-5 agonist
Simvastatin	HMG CoA reductase inhibitor
Triazolam	Benzodiazepine
Voriconazole	Anti-fungal

Source:

FDA guidance drug interaction studies: study design, data analysis, and implications for dosing and labeling, 2006.

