- Abnormal QTcB ( $\geq 450$  msec in males and  $\geq 470$  msec in females)
- Ejection fraction  $\leq 50\%$  as assessed by echocardiogram.

3.2.13 Uncontrolled hypertension (Diastolic blood pressure  $> 100$  mmHg; Systolic blood pressure  $> 150$  mmHg).

3.2.14 History of venous thromboembolism (e.g. deep venous thrombosis or pulmonary embolism) within 6 months of study entry. Note: Participants enrolled after this window must be on appropriate therapeutic anticoagulation.

3.2.15 Taking medications that are known to be associated with Torsades de Pointes. Medications include but are not limited to:

- Quinidine, procainamide, disopyramide
- Amiodarone, sotalol, ibutilide, dofetilide
- Erythromycins, clarithromycin
- Chlorpromazine, haloperidol, mesoridazine, thioridazine, pimozide
- Zyprasi done, cisapride, bepridil, droperidol, methadone, arsenic
- Chloroquine, domeperidone, halofantrine, levomethdyl, pentamidine
- Sparfloxacin, lidoflazine

**Note:** Participants who have taken a medication associated with Torsades de Pointes will still be eligible for participation if the medication is discontinued at least 14 days before the initiation of study treatment.

3.2.16 Ongoing active infection. The requirement for intravenous (IV) antibiotics is considered active infection.

3.2.17 Known history of human immunodeficiency virus (HIV). Testing is not required in the absence of history.

3.2.18 Pregnant or breastfeeding.

3.2.19 Diagnosed with or received anti-cancer therapy for another primary malignancy within 3 years prior to entry (except for non-melanoma skin cancer or in situ cancers).

3.2.20 Any condition or illness that, in the opinion of the Investigator, would compromise patient safety or interfere with the evaluation of the drug.

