### **5.8 Duration of Therapy / Subject Discontinuation**

Duration of therapy will depend on individual response, evidence of disease progression and tolerance. Treatment will continue until one of the following:

- Intolerable toxicity as determined by the Investigator.
- Progression of disease requiring an alternative therapy. Note: In some cases, despite disease progression by RECIST criteria, participants may be continued on study drug if deemed beneficial by the participant and investigators as well as approval from the Principal Investigator/Sponsor.
- Entry into another therapeutic clinical trial or implementation of another anti-cancer therapy.

- Significant deviation from the protocol or eligibility criteria, in the opinion of the Investigator.
- Noncompliance with study or follow-up procedures.
- Withdrawal of participant consent.
- Termination of the trial by the Principal Investigator/Sponsor.
- Any other reason that, in the opinion of the Investigator, would justify removal of the participant from the study.

In the event that a participant is withdrawn from the study, every effort will be made by the Investigator to document and report the reason(s) for withdrawal as thoroughly as possible. The reason(s) for withdrawal must be clearly reported on the appropriate page of the participant's electronic case report form (eCRF). An eCRF must be completed for any participant who receives study drug. An End-of-Treatment reason must be recorded for any participant who receives study medication.

If a participant is discontinued from the trial for any reason, every effort must be made to perform all End of Treatment assessments per the schedule of events. In the event that the participant fails to return for the necessary visit(s), an effort must be made to contact the participant to determine the reason, and this information should be recorded in the appropriate source record and reported as a deviation. All participants who discontinue prematurely from the active study period will be followed for PFS and survival at least every 3 months ( $\pm$  14 days), up to 2 years after the initial dose of ponatinib.

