### **6.13 Prohibited Treatment**

The following concurrent medications and treatments are prohibited:

- Any other anti-cancer therapy including, but not limited to, chemotherapeutic agents, immunotherapy, biological response modifiers, surgery and/or systemic hormonal therapy (hematopoietic growth factors are permitted).
- Use of any other investigational drug or device.
- Use of medications that are known to be associated with the development of Torsades de Pointes (see [Appendix B](#)).
- Herbal preparations or related over-the-counter preparations containing herbal ingredients either during or within 2 weeks prior to the first dose of ponatinib.
- Elective surgery requiring in-patient care.

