### **6.14 Treatments to be Used with Caution**

Medications that are potent substrates, inhibitors or inducers of P450 cytochromes, in particular CYP3A4 (see [Appendix C](#)), should be avoided when possible but are not prohibited.

Medications that prolong the QTcB interval should be avoided when possible but are not prohibited. If such medications are deemed necessary and used while a participant is on study, additional ECG monitoring should be performed as clinically indicated.

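### Clarithromycin is banned by Section 6.13 and Appendix B, yet Section 6.14 and Appendix C treat it as usable with caution

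*Combined protocol and SAP*

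**What the plan says.** Three places in the protocol rule clarithromycin out.

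- Section 6.13 includes among prohibited treatments "Use of medications that are known to be associated with the development of Torsades de Pointes" and refers the reader to Appendix B.
- Appendix B lists clarithromycin under a heading that contains the words "Risk of Causing Torsades de Pointes and Prohibited in this Study".
- Exclusion criterion 3.2.15 lists "Erythromycins, clarithromycin" among the drugs that bar entry. Its note allows entry only if the drug was stopped at least 14 days before study treatment.

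Two places treat it as usable.

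- Appendix C, the list of drugs with a known CYP3A4 interaction, opens with "The following medications should be used with caution" and includes clarithromycin.
- Section 6.14 has two paragraphs. The first covers drugs acting on P450 cytochromes, cites Appendix C, and says they "should be avoided when possible but are not prohibited". The second reads: "Medications that prolong the QTcB interval should be avoided when possible but are not prohibited". It asks for extra ECGs, when clinically warranted, if such a drug is used.

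**The concern.** A site choosing an antibiotic for a participant on ponatinib gets opposite answers depending on where it looks. Section 6.13 and Appendix B forbid clarithromycin. Section 6.14 and Appendix C discourage it but leave it open. The QT paragraph of 6.14 has the same gap in general form. Appendix B is titled as a list of prohibited drugs that affect the QT interval, so the statement that QT-prolonging drugs are not prohibited literally covers the drugs Appendix B prohibits.

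The rule concerned is a cardiac safeguard. Section 7 counts QTc prolongation among the expected toxicities of ponatinib, and Section 6.15 warns that a drug with both QT and CYP3A4 effects may worsen the QTc problem. By the protocol's own lists, clarithromycin is such a drug. Several institutions will enrol, and under the monitoring plan (Appendix D, 3.9) an unapproved departure from the protocol is a reportable violation. Sites therefore need one answer.

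**Working it through.** The plan states no figure on this point, so the check compares lists and reads the sections against each other.

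**Inputs.** Drugs named in Appendix B: 28. Drugs named in Appendix C: 26. Drugs named in criterion 3.2.15: 27.

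**Overlap by name.**

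- Appendix B and Appendix C share 1 drug: clarithromycin.
- Criterion 3.2.15 and Appendix C share 1 drug: clarithromycin.
- Erythromycin is in Appendix B and 3.2.15 but not in Appendix C, so it raises no conflict through Appendix C.

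**Status of clarithromycin by section.**

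| Place | Status |
|---|---|
| 3.2.15 | Excludes at entry unless stopped at least 14 days before treatment |
| 6.13 with Appendix B | Prohibited on study |
| 6.14, CYP3A4 paragraph, with Appendix C | Avoid if possible; not prohibited |
| 6.14, QT paragraph | Avoid if possible; not prohibited, for QT-prolonging drugs generally |
| Appendix C | Use with caution |

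**Search for a rule of precedence.** Four places come near to one.

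- Section 5.1, item 13, asks for ECG monitoring with QT-prolonging drugs and sets aside those explicitly prohibited. That is the distinction 6.14 lacks, but it sits inside an ECG instruction.
- Section 6.15 recognises that some QT drugs also interact with CYP3A4. It does not give their status.
- Section 7.5.10 calls for medication review and withdrawal of QT-prolonging drugs, but only once prolongation has been seen.
- Appendix C refers questions to the medical monitor and does not flag the conflict.

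None says which rule governs a drug that falls under both. Of the 2 sentences in 6.14 that say drugs are not prohibited, 0 except drugs banned elsewhere.

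**Would deletion alone be enough?** Removing clarithromycin leaves 26 − 1 = 25 drugs in Appendix C, none of them in Appendix B. The QT paragraph of 6.14 would still contradict Appendix B, and Appendix C describes itself as incomplete. An exception clause is therefore needed whether or not the line is deleted.

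**Effect on the design.** The rule in Section 13.1 (at least 4 responses in 20) has type I error P(X ≥ 4 | n = 20, p = 0.10) = 0.133 and power P(X ≥ 4 | n = 20, p = 0.30) = 0.893. These match the stated 13% and 89%. No input to either figure depends on the concomitant-medication rules.

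**The case against.** The best reply is that there is no real conflict. Appendix B and Appendix C address different risks, and the first paragraph of 6.14 can be read as saying that a drug is not prohibited on CYP3A4 grounds. A caution does not authorise what another section bans by name, and a site satisfies every section by not giving clarithromycin. Section 6.13 stands immediately before 6.14, and Appendix B immediately before Appendix C. Criterion 3.2.15 is checked at registration, and Table 8-1 calls for concomitant medications to be recorded at every scheduled treatment visit. The wording of 5.1, item 13, shows that the authors had the distinction in mind.

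Much of this stands. It establishes the likely intent and makes misuse improbable. It does not remove the contradiction. Neither paragraph of 6.14 limits itself to one ground, and an instruction to use a named drug with caution presupposes that it may be used. The later safeguards are also looser than a ban. Routine ECGs fall only at screening, Cycles 4, 7 and 13 (Day 1) and end of treatment. Extra ECGs under 6.14 are left to clinical judgement, and the ECG instruction in 5.1 is worded for drugs that are not explicitly prohibited.

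A reader might infer a second contradiction from imatinib, which Appendix C lists as an anti-leukemia drug. The documents do not support giving that weight. Section 6.13 bars "Any other anti-cancer therapy including, but not limited to, chemotherapeutic agents", and Section 5.8 ends study treatment on "Entry into another therapeutic clinical trial or implementation of another anti-cancer therapy". The opening of Section 6 bars other agents given to treat the participant's malignancy. Criterion 3.2.19 excludes another primary malignancy diagnosed or treated within 3 years, apart from non-melanoma skin cancer and in situ cancers, so a reason to give imatinib would hardly arise.

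**Conclusion.** The point holds as a minor internal contradiction in a cardiac-safety rule. One named drug is both prohibited and described as not prohibited, and the QT paragraph of 6.14 lacks an exception for Appendix B. It should be corrected, at low priority.

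Two larger conclusions would go too far. The first is that 6.14 cancels the Appendix B ban. Section 6.13, the Appendix B heading, criterion 3.2.15 and the wording of 5.1, item 13, all point to the stricter rule, and a careful site would probably follow it. The second is that the overlap measures risk to participants. A count of shared list entries says nothing about how often clarithromycin would be given or with what effect. The documents do not say how often a site would rely on Appendix C alone, and they give no interaction data for clarithromycin with ponatinib.

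The conclusion rests only on the current wording of the sections named and on the drug names as listed. It has no bearing on sample size, power or the primary analysis.

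**What to change.** Add one exception to both paragraphs of Section 6.14 and to the opening of Appendix C: *except drugs prohibited under Section 6.13 or Appendix B, which remain prohibited*. In addition, either delete clarithromycin from Appendix C or keep it there marked *prohibited, see Appendix B*. Marking it has the advantage of keeping the CYP3A4 information visible.

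The cost is a few words in three places and one edited table line, with no added patients, visits or procedures. Section 12.1 requires IRB approval of any protocol change before it is implemented, and Appendix D (3.2 and 3.4) gives participating institutions 90 days for theirs. The change does not justify an amendment of its own and is best bundled with the next one.

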## **1.0 INTRODUCTION**

The Dana-Farber/Harvard Cancer Center Multi-Center Data and Safety Monitoring Plan (DF/HCC DSMP) outlines the procedures for conducting a DF/HCC Multi-Center research protocol. The DF/HCC DSMP should serve as a reference for any sites external to DF/HCC that will be participating in the research protocol.

### **1.1 Purpose**

To establish standards that will ensure that a Dana-Farber/Harvard Cancer Center Multi-Center protocol will comply with Federal Regulations, Health Insurance Portability and Accountability Act (HIPAA) requirements and applicable DF/HCC Standard Operating Procedures.

### **1.2 Multi-Center Data and Safety Monitoring Plan Definitions**

**DF/HCC Multi-center Protocol:** A research protocol in which one or more outside institutions are collaborating with Dana-Farber/Harvard Cancer Center where a DF/HCC investigator is the sponsor. DF/HCC includes Dana-Farber/Partners Cancer Care (DF/PCC) Network Clinical Trial Affiliates.

**Lead Institution:** One of the Dana-Farber/Harvard Cancer Center consortium members (Dana-Farber Cancer Institute (DFCI), Massachusetts General Hospital (MGH), Beth Israel Deaconess Medical Center (BIDMC), Children's Hospital Boston (CHB), Brigham and Women's Hospital (BWH)) responsible for the coordination, development, submission, and approval of a protocol as well as its subsequent amendments per the DFCI IRB and applicable regulatory guidelines (CTEP, Food and Drug Administration (FDA), Office of Biotechnology Activities (OBA) etc.). The Lead Institution is typically the home of the DF/HCC Sponsor. The Lead Institution also typically serves as the Coordinating Center for the DF/HCC Multi-Center Protocol.

**DF/HCC Sponsor:** The person sponsoring the submitted Multi-Center protocol. Within DF/HCC, this person is the Overall Principal Investigator who takes responsibility for initiation, management and conduct of the protocol at all research locations. In applicable protocols, the DF/HCC Sponsor will serve as the single liaison with any regulatory agencies (i.e. CTEP Protocol and Information Office (PIO), FDA, OBA etc.). The DF/HCC Sponsor has ultimate authority over the protocol and is responsible for the conduct of the study at DF/HCC and all Participating Institutions. In most cases the DF/HCC Sponsor is the same person as the DF/HCC Principal Investigator; however, both roles can be filled by two different people.

**Participating Institution:** An institution that is outside the DF/HCC and DF/PCC consortium that is collaborating with DF/HCC on a protocol where the sponsor is a DF/HCC

Investigator. The Participating Institution acknowledges the DF/HCC Sponsor as having the ultimate authority and responsibility for the overall conduct of the study.

**Coordinating Center:** The entity (i.e. Lead Institution, Medical Monitor, Contract Research Organization (CRO), etc.) that provides administrative support to the DF/HCC Sponsor in order that he/she may fulfill the responsibilities outlined in the protocol document and DSMP, and as specified in applicable regulatory guidelines (i.e. CTEP Multi-Center Guidelines). In general, the Lead Institution is the Coordinating Center for the DF/HCC Multi-Center Protocol. Should the DF/HCC Sponsor decide to use a CRO, the CRO will be deemed the Coordinating Center.

**DF/HCC Quality Assurance Office for Clinical Trials:** A unit within DF/HCC developed to computerize and manage data, and to provide a Quality Control and Quality Assurance function for DF/HCC trials.

## 2.0 GENERAL ROLES AND RESPONSIBILITIES

For DF/HCC Multi-Center Protocols, the DF/HCC Sponsor, the Coordinating Center, and the Participating Institutions are expected to adhere to the following general responsibilities:

### 2.1 DF/HCC Sponsor

The DF/HCC Sponsor, [name] will accept responsibility for all aspects of conducting a DF/HCC Multi-Center protocol which includes but is not limited to:

- Oversee the coordination, development, submission, and approval of the protocol as well as subsequent amendments.
- Ensure that the investigators, study team members, and Participating Institutions are qualified and appropriately resourced to conduct the protocol.
- Submit the Multi-Center Data and Safety Monitoring Plan as an appendix to the protocol.
- Ensure all Participating Institutions are using the correct version of the protocol.
- Ensure that each participating investigator and study team receives adequate protocol training and/or a Site Initiation Visit prior to enrolling participants and throughout trial's conduct as needed.
- Ensure the protocol will be provided to each participating site in a language understandable to all site personnel when English is not the primary language.
- Monitor progress and overall conduct of the study at all Participating Institutions.
- Ensure all DFCI Institutional Review Board (IRB), DF/HCC and other applicable (i.e. FDA) reporting requirements are met.
- Review data and maintain timely submission of data for study analysis.
- Act as the single liaison with FDA (investigator-held IND trials), as applicable.
- Ensure compliance with all requirements as set forth in the Code of Federal Regulations, applicable DF/HCC requirements, HIPAA requirements, and the approved protocol.

- Commit to the provision that the protocol will not be rewritten or modified by anyone other than the DF/HCC Sponsor.
- Identify and qualify Participating Institutions and obtain accrual commitments prior to extending the protocol to that site.

## **2.2 Coordinating Center**

The Coordinating Center will assume the following general responsibilities:

- Assist in protocol development
- Maintain copies of Federal Wide Assurance and Institutional Review Board (IRB) approvals from all Participating Institutions.
- Maintain FDA correspondence, as applicable.
- Maintain updated roster of participants.
- Verify eligibility.
- Verify response.
- Oversee the data collection process from Participating Institutions.
- Maintain documentation of Serious Adverse Event (SAE) reports submitted by Participating Institutions and submit to DF/HCC Sponsor for timely review.
- Distribute adverse events reported to the DF/HCC Sponsor that fall under the DFCI IRB Adverse Event Reporting Policy to all participating investigators.
- Provide Participating Institutions with information regarding DF/HCC requirements that they will be expected to comply with.
- Monitor Participating Institutions either by on-site or virtual monitoring.
- Maintain Regulatory documents of all Participating Institutions.
- Conduct regular communications with all Participating Institutions (conference calls, emails, etc).
- Maintain documentation of all communications.
- Ensure that each Participating Institution has the appropriate assurance on file with the Office of Human Research Protection (OHRP).

## **2.3 DF/HCC Quality Assurance Office for Clinical Trials (QACT)**

In addition to the Coordinating Center, the DF/HCC QACT provides the following support services to assist the DF/HCC Sponsor:

- Develop protocol specific case report forms (CRF/eCRFS).
- QA/QC data of protocol specific CRFs.
- Provide a central participant registration, which includes review of consent and eligibility.
- Provide auditing services (funding and QACT approval required).

## **2.4 Participating Institution**

Each Participating Institution is expected to comply with all applicable Federal Regulations and DF/HCC requirements, the protocol and HIPAA requirements. All Participating Institutions will provide a list of personnel assigned to the role for oversight of data management at their site to the Coordinating Center.

The general responsibilities for each Participating Institution are as follows:

- Commit to the accrual of participants to the protocol.
- Submit protocol and/or amendments to their local IRB.
- Maintain a regulatory binder in accordance with DF/HCC requirements.
- Provide the Coordinating Center with regulatory documents as requested.
- Participate in protocol training prior to enrolling participants and throughout the trial as needed (i.e. teleconferences).
- Update Coordinating Center with research staff changes on a timely basis.
- Register participants through the Coordinating Center.
- Submit source documents, research records, and CRFs per protocol specific submission guidelines to the Coordinating Center.
- Submit Serious Adverse Event (SAE) reports to local IRB per local requirements and to the Coordinating Center, in accordance with DF/HCC requirements.
- Submit protocol deviations and violations to local IRB per local requirements and to the DF/HCC Sponsor in accordance with DF/HCC requirements.
- Secure and store investigational agents and/or other protocol mandated drugs per federal guidelines and protocol requirements.
- Have office space, office equipment, and internet access that meet HIPAA standards.
- For protocols using investigational agents, the Participating Institution will order their own investigational agents regardless of the supplier (i.e. National Cancer Institute (NCI), pharmaceutical company).

